15.1 Data Sets Analyzed

All eligible subjects will be included in each analysis.

15.2 Demographic and Baseline Characteristics

Demographic information (date of birth, gender, income, education, professional status, and social status) will be recorded at screening.

15.3 Analysis of Primary Endpoint

ANOVA

15.4 Analysis of Secondary Endpoints

ANOVA

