3.2 Secondary Objectives

1. Evaluate the anti-obesity effect of multi-Strain probiotic supplementation
2. Investigate the effect of probiotics on reducing Lipopolysaccharides LPS.
3. Determine the effect of probiotics on liver functions.
4. Study the association between probiotics and food intake.
5. Evaluate the role of gender difference in response to probiotic.

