5.2 Secondary Efficacy Endpoints

Other obesity-related outcomes included body weight, WC, and hip circumference (HC).

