5.3 Safety Evaluations

- Increasing in Antioxidants enzymes including superoxide dismutase (SOD), catalase, and glutathione peroxidase (GPx).
- Decreasing in both Aspartate Transaminase (AST) and Alanine transaminase (ALT).
- Decreasing in lipopolysaccharide LPS, which is known also as endotoxin.
- Decreasing in blood analysis including glycated hemoglobin (HA1c) and lipid profile (TC, HDL-C, and TG)

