9.2.2 Blood Chemistry Profile

The blood analysis including glycated hemoglobin (H_{A1c}) and lipid profile (TC, HDL-C, and TG). Other blood analysis include: LPS, Aspartate Transaminase (AST), Alanine transaminase (ALT), superoxide dismutase (SOD), catalase, and glutathione peroxidase (GPx).

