15 STATISTICAL METHODS AND CONSIDERATIONS

The primary outcome of this study is the difference in waist circumference between groups after 12 weeks of supplementation. The analysis of this study will include all the patients using intention to treat (ITT) methodology. Waist circumference of two groups after 12 weeks of supplementation will be examined for statistical significant using repeated measures ANOVA.

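### LPS, liver enzymes and triglycerides have no analysis beyond the one word ANOVA in 15.4, which is not expressly tied to them; if they are right-skewed, an untransformed analysis loses power

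*Combined protocol and SAP*

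**What the plan says.** Section 3.2 (and the synopsis) sets two biomarker objectives: "Investigate the effect of probiotics on reducing Lipopolysaccharides LPS" and "Determine the effect of probiotics on liver functions". Section 9.2.2 lists the blood measurements, including LPS, AST, ALT and TG. Sections 9.3, 10.1 and 10.2 have blood taken at baseline and at the end of the three months, so each marker has two values per participant.

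The method is much thinner. The whole text under "15.4 Analysis of Secondary Endpoints" is the word ANOVA. Section 15 is fuller, but only for waist circumference (WC), which "will be examined for statistical significant using repeated measures ANOVA". No section mentions a transformation, a rank-based method, a check of distribution, an outlier rule or a baseline covariate.

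The endpoint lists do not close the gap. Section 5.2 reads "Other obesity-related outcomes included body weight, WC, and hip circumference (HC" and names no blood marker. Section 5.3, headed Safety Evaluations, states the markers as hoped-for changes, for example "Decreasing in both Aspartate Transaminase (AST) and Alanine transaminase (ALT". TG appears in 5.3 and 9.2.2 but in no secondary objective.

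**The concern.** Concentrations and enzyme activities cannot be negative, and their spread often grows with their level. If that holds here, ANOVA on untransformed values compares arithmetic means that a few high participants can dominate. Those participants also inflate the residual variance, so a real proportional reduction is easier to miss, and one result can depend on one or two people among 90.

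Two stated objectives rest on these markers, and section 15.6 gives a sample size for WC only, so they have no power target. A one-word plan also leaves the scale, and the choice between end-of-study value and change, open until the data are seen.

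**Working it through.** **The plan's own figure.** The only sample-size figure is 17 per group for WC (95% power, 5% type I error), raised to 45. No effect size, SD or sidedness is given, so it cannot be reproduced. Solved backwards, two-sided with the normal approximation, it implies a standardized difference of (1.96 + 1.645) × √(2/17) = 1.24. It says nothing about the blood markers.

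**Inputs.** From the documents: 45 per arm (15.6), 1:1 allocation (8.1), two visits. Assumed: log-normal values, log-SD σ from 0.4 to 1.0, a proportional effect, two-sided 5% level, no dropout and, where baseline is used, a log-scale correlation of 0.6 between visits. The coefficient of variation is CV = √(exp(σ²) − 1).

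**Effect scaled to the spread.** The log-scale effect is 2.80 × σ × √(2/45) = 0.590σ, so the ratio of means is exp(−0.590σ). Log-scale power is about Φ(2.80 − 1.96) = 80%, or 79% with the t distribution. Simulated power for end-of-study values (simulation error up to about one point):

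| σ (CV) | Ratio | Untransformed | Log | Loss |
|---|---|---|---|---|
| 0.4 (42%) | 0.79 | 76% | 79% | 3 |
| 0.6 (66%) | 0.70 | 73% | 80% | 7 |
| 0.8 (95%) | 0.62 | 68% | 79% | 11 |
| 1.0 (131%) | 0.55 | 60% | 79% | 19 |

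**Fixed effect.** The larger losses above go with reductions of 30% to 45%. Holding the reduction constant, untransformed v log power is:

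| Reduction | σ 0.4 | σ 0.6 | σ 0.8 | σ 1.0 |
|---|---|---|---|---|
| 10% | 22 v 24% | 11 v 13% | 8 v 9% | 6 v 8% |
| 15% | 45 v 48% | 21 v 25% | 13 v 16% | 9 v 12% |
| 21% | 76 v 79% | 39 v 45% | 23 v 28% | 14 v 20% |

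Before rounding, the 15% row loses about 3 points at every σ.

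**If ANOVA means repeated measures.** With two visits, the group-by-time test is a comparison of change. The SD of log change is σ√(2(1 − 0.6)) = 0.894σ, and scaling the effect to that SD gives ratios of exp(−0.528σ). Power for untransformed v log change is 69 v 79%, 60 v 79%, 50 v 79% and 41 v 80%, a loss of about 10 to 39 points. For a fixed 15% reduction the same comparison loses about 9, 7, 6 and 5 points.

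**The proposed model.** Adjusting for log baseline multiplies the residual variance by 1 − 0.6² = 0.64. At the effects in the first table, the standardized effect rises from 2.80 to 2.80/0.8 = 3.5, and power is about Φ(3.5 − 1.96) = 94%; simulation gives about 93%. The gain from 79% to 93% comes from the baseline covariate, not from the log scale.

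**Type I error.** With no effect, untransformed tests rejected in 4.1% to 5.0% of trials over CV 0.3 to 1.5.

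**Influence of high values.** Over CV 0.3 / 0.5 / 0.8 / 1.0 / 1.5, the two largest of 90 values carry a median 20 / 25 / 34 / 39 / 49% of the total sum of squares, against 14% for normal data. Removing them changes significance at 5% in 12 / 15 / 18 / 22 / 24% of trials, against 10% for normal data.

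**The case against.** Several objections have force.

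- **Coverage.** Section 15.4 concerns secondary endpoints, and 5.2 restricts those to body weight, WC and hip circumference (HC). A reader might infer that the plan has prescribed untransformed ANOVA for the blood markers. It has not: neither the link nor the scale is stated, and an ANOVA of log values is still ANOVA. This stands, but it does not rescue the plan. Either 15.4 covers the markers without a scale, or two objectives have no analysis; both call for the same edit.
- **Skewness is assumed.** The documents give no mean, SD or distribution. Participants are aged 19 to 40 and should be free of chronic disease needing medication (6.2, 7.1), which may shorten the upper tail. At CV 0.3 the end-of-study loss is only about 2 points (78% v 80%).
- **The set-up favours logs.** Log-normal data with a proportional effect suit the log analysis by construction, and the scaled effects grow with the spread. With modest fixed effects, low power comes mainly from variability and sample size.
- **False positives.** A reader might infer that a few extreme values will produce spurious findings more often than 5% of the time. The null simulations show the opposite: error rates sit at or slightly below nominal. What remains is that a single result can be sensitive to a few values.

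**Conclusion.** The point holds as a weakness in the analysis of secondary outcomes. The plan gives LPS, AST, ALT and TG nothing beyond one word that is not expressly tied to them. If they are right-skewed, untransformed ANOVA of end-of-study values loses about 3 to 19 power points over log-SD 0.4 to 1.0 with the effect scaled to about 80% log-scale power. The loss is about 3 points for a fixed 15% reduction, and larger if change from baseline is analysed.

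These sizes rest on log-normality, a proportional effect and 45 completers per arm; the figures for change and for baseline adjustment also rest on the correlation of 0.6. None but the planned 45 comes from the documents. The upper end should not be read as the expected loss, since it needs a reduction of about 45%. The primary WC analysis and the sample size are unaffected.

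**What to change.** In 15.4, name LPS, AST, ALT and TG as outcomes. Analyse each with a linear model of the log Visit 2 value on treatment and log baseline, and report the geometric mean ratio (probiotic/placebo) with 95% CI. State how values below an assay's detection limit enter the log.

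Keep body weight, WC, HC, HbA1c, TC and HDL-C untransformed, with the baseline value as covariate. Log-transform SOD, catalase and GPx only if blinded pooled data show skew, and record that decision before unblinding.

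The cost is a few lines of text and no new data. The downside is that results for the logged markers are ratios, not differences in units; a ratio can be presented as a percentage change.

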15.5 Interim Analysis

All analysis will be done at the end of the intervention.

15.6 Sample Size and Randomization

The study population depends on the study result of Gomes and his colleagues who used the G-Power software (version 3.0.10) to calculate the sample size. The primary outcome in that study is the difference in waist circumference between groups. The power calculation requires 17 participants in each group (95% power; 5% type I error) to detect a difference in waist circumference (Gomes et al, 2018). In this study, to avoid any later drop-off, both groups will be set to have 45 participants.

16 DATA COLLECTION, RETENTION AND MONITORING

16.1 Data Collection Instruments

The Investigator will prepare and maintain adequate and accurate source documents designed to record all observations and other pertinent data for each subject treated with the study drug.

Study personnel at each site will enter data from source documents corresponding to a subject's visit into the protocol-specific electronic, Case Report Form (eCRF) and paper CRF when the information corresponding to that visit is available. Subjects will not be identified by name in the study documents to be collected by the Sponsor (or designee) but will be identified by a subject number.

For eCRFs: If a correction is required for an eCRF, the time and date stamps track the person entering or updating eCRF data and creates an electronic audit trail. For paper CRFs: If a correction is made on a CRF, the study staff member will line through the incorrect data, write in the correct data and initial and date the change.

The Investigator is responsible for all information collected on subjects enrolled in this study. All data collected during the course of this study must be reviewed and verified for completeness and accuracy by the Investigator

Data Management Procedures

The data will be kept in paper documents and e-documents, the study doesn't have database.

16.2 Data Quality Control and Reporting

Inapplicable

16.3 Archival of Data

All data will be kept in both:

Electronic documents, in which can be reached by principal investigator and other investigators only.

Paper documents which can be kept in a locked file cabinet until 2 years at least after the study, then they will be disposed.

16.4 Availability and Retention of Investigational Records

The Investigator must make study data accessible to the monitor, other authorized representatives of the Sponsor (or designee), as IRB and S FDA, inspectors upon request. A file for each subject must be maintained that includes the signed Informed Consent, and copies of all source documentation related to that subject. The Investigator must ensure the reliability and availability of source documents from which the information on the CRF was derived.

All study documents (patient files, signed informed consent forms, copies of CRFs, Study File Notebook, etc.) must be kept secured for a period of two years following study. There may be other circumstances for which the Sponsor is required to maintain study records and, therefore, the Sponsor should be contacted prior to removing study records for any reason.

16.5 Monitoring

Appropriate regulatory authorities, such as the SFAD and Clinic Manager, may conduct monitoring visits to conduct on-site monitoring and/or audits of all appropriate study documents.

16.6 Subject Confidentiality

In order to maintain subject confidentiality, only a site number, subject number and subject initials will identify all study subjects on CRFs and other documentation submitted to the Sponsor. Additional subject confidentiality issues (if applicable) are covered in the Clinical Study Agreement.

17 ADMINISTRATIVE, ETHICAL, REGULATORY CONSIDERATIONS

To maintain confidentiality, all laboratory specimens, evaluation forms, reports and other records will be identified by a coded number and initials only. All study records will be kept in a locked file cabinet and code sheets linking a patient's name to a patient identification number will be stored separately in another locked file cabinet. Clinical information will not be released without written permission of the subject, except as necessary for monitoring by the SFDA. The Investigator must also comply with all applicable privacy regulations.

17.1 Protocol Amendments

Any amendment to the protocol will be written by the Sponsor. Protocol amendments cannot be implemented without prior written IRB approval except as necessary to eliminate immediate safety hazards to patients. A protocol amendment intended to eliminate an apparent immediate hazard to patients may be implemented immediately, provided the IRBs are notified within five working days.

17.2 Institutional Review Boards and Independent Ethics Committees

The protocol and consent form are reviewed and approved by the IRB prior to study initiation. Serious adverse experiences regardless of causality will be reported to the IRB in accordance with the standard operating procedures and policies of the IRB, and the Investigator will keep the IRB informed as to the progress of the study. The Investigator will obtain assurance of IRB compliance with regulations.

Any documents that the IRB may need to fulfill its responsibilities (such as protocol, protocol amendments, Investigator's Brochure, consent forms, information concerning patient recruitment, payment or compensation procedures, or other pertinent information)

will be submitted to the IRB. The IRB written unconditional approval of the study protocol and the informed consent form will be in the possession of the Investigator before the study is initiated. The IRB unconditional approval statement will be transmitted by the Investigator to the Sponsor or designee prior to the shipment of study supplies to the site. This approval must refer to the study by exact protocol title and number and should identify the documents reviewed and the date of review.

Protocol and/or informed consent modifications or changes may not be initiated without prior written IRB approval except when necessary to eliminate immediate hazards to the patients or when the change(s) involves only logistical or administrative aspects of the study. Such modifications will be submitted to the IRB and written verification that the modification was submitted and subsequently approved should be obtained.

The IRB must be informed of revisions to other documents originally submitted for review; serious and/or unexpected adverse experiences occurring during the study in accordance with the standard operating procedures and policies of the IRB; new information that may affect adversely the safety of the patients of the conduct of the study; an annual update and/or request for re-approval; and when the study has been completed.

17.3 Informed Consent Form

The Investigator will prepare the informed consent form and provide the documents to the Sponsor or designee for approval prior to submission to the IRB. The consent form generated by the Investigator must be acceptable to the Sponsor and be approved by the IRB. The written consent document will embody the elements of informed consent as described in the International Conference on Harmonisation and will also comply with local regulations. The Investigator will send an IRB -approved copy of the Informed Consent Form to the Sponsor (or designee) for the study file.

A properly executed, written, informed consent will be obtained from each subject prior to entering the subject into the trial. Information should be given in both oral and written form and subjects must be given ample opportunity to inquire about details of the study. If appropriate and required by the local IRB, assent from the subject will also be obtained. A copy of the signed consent form will be given to the subject or legal representative of the subject and the original will be maintained with the subject's records.

17.4 Publications

The preparation and submittal for publication of manuscripts containing the study results shall be in accordance with a process determined by mutual written agreement among the study Sponsor and participating institutions. The publication or presentation of any study results shall comply with all applicable privacy laws.

17.5 Investigator Responsibilities

By signing the Agreement of Investigator form, the Investigator agrees to:

1. Conduct the study in accordance with the protocol and only make changes after notifying the Sponsor (or designee), except when to protect the safety, rights or welfare of subjects.
2. Personally conduct or supervise the study (or investigation).
3. Ensure that the requirements relating to obtaining informed consent and IRB review and approval meet federal guidelines.
4. Report to the Sponsor or designee any AEs that occur in the course of the study.
5. Ensure that all associates, colleagues and employees assisting in the conduct of the study are informed about their obligations in meeting the above commitments.
6. Maintain adequate and accurate records and to make those records available for inspection with the Sponsor (or designee).
7. Ensure that an IRB that complies with the.
8. Promptly report to the IRB and the Sponsor (or designee) all changes in the research activity and all unanticipated problems involving risks to subjects or others (to include amendments and IND safety reports).
9. Seek IRB approval before any changes are made in the research study, except when necessary to eliminate hazards to the patients/subjects.
10. Comply with all other requirements regarding the obligations of clinical investigators and all other pertinent requirements.

APPENDIX 1. EXAMPLE OF SCHEDULE OF STUDY VISITS

	VISIT 1 (Day/Week/Month #) ^a	VISIT 2 (Day/Week/Month #) ^a
Informed Consent	X	
Medical History	X	
Complete Physical Exam	X	
Abbreviated Physical Exam		X
Height	X	X
Weight	X	X
Vital Signs	X	X
Oximetry		
Spirometry		
Pharmacokinetics		X
Chemistry	X	X
Pregnancy Test (Urine or Serum)		
Hematology		
ESR		
C-Reactive Protein		
Urinalysis		
Randomization	X	
Dispensing or Administration of Study Drug	X	X
Counting of Returned Study Drug		X
Initiate Subject Diary	X	

Subject Diary Review		X
Concomitant Medication Review	X	X
Adverse Experiences		

^a ±2 days

Required Components of Informed Consent

Informed consent is not a single event or just a form to be signed; it is an educational process that takes place between the investigator and the prospective subject. The basic elements of the consent process include:

full disclosure of the nature of the research and the participant's involvement, adequate comprehension on the part of the potential participant, and the participant's voluntary choice to participate.

It is the investigator's responsibility to document that the informed consent process has taken place, and an informed consent form is the standard for documenting the process for research projects involving human participants.

Consent forms must contain all the required components of informed consent as defined in SOP 9: Informed Consent Options, Processes, and Documentation and summarized below. The consent form must be written in language that is easy for a potential participant to understand and assures that individual's comprehension. Therefore, avoiding technical terms and complex sentences, even for the educated layperson, is very important.

When the participant population is not homogeneous, different consent documents may be required for different groups of people. If the research population will include participants under 18 years of age, then the IRB will expect investigators to use an assent form and a parental permission form instead (see SOP 11: Informed Consent, Enrollment, and Other Considerations for Research Involving Children). Similarly, research with cognitively or decisionally impaired individuals will require documented consent from another party—namely that person's legally authorized representative (see SOP 9, section 8 and/or SOP 10: xxx).

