8.7 Measures of Treatment Compliance

Subjects will be asked to keep a participant's diary noting the day and date they take their study probiotic supplement and any adverse events. They will be asked to bring their diary to next study visit along with all used and unused probiotic or placebo sachets.

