9.1.9 Adverse Events

Information regarding occurrence of adverse events will be captured throughout the study. Duration (start and stop dates and times), severity/grade, outcome, treatment and relation to the supplementation will be recorded on the case report form (CRF).

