10.2 Visit 2 at the end of the study (3 months length)

1. Perform an abbreviated physical examination
2. Perform and record results of blood pressure testing.
3. Collect blood for clinical laboratory.
4. Taking 24-hour record
5. Taking anthropometric measurements.
6. Taking physical activities.

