10.3 Early Withdrawal Visit

1. Record any Adverse Experiences and/or review subject diary for adverse experiences and exclusionary medication use.
2. Record changes to concomitant medications.
3. Perform complete physical examination.
4. Perform and record vital signs.

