11.2 Serious Adverse Experiences (SAE)

Using probiotic products doesn't cause any SAE.

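### No active adverse-event enquiry is scheduled for completers at Visit 2, although 9.1.9 requires capture throughout; separately, 11.1 and 11.2 prejudge severity and causality

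*Combined protocol and SAP*

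**What the plan says.** **General rule.** Section 9.1.9 states: "Information regarding occurrence of adverse events will be captured throughout the study". It asks for dates, severity, outcome, treatment and relation to the supplement on the case report form.

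**Diary.** Under 8.7 every participant keeps a "diary noting the day and date they take their study probiotic supplement and any adverse events", and brings it with used and unused sachets to the next visit.

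**Schedule.** Section 9 presents Appendix 1 as the schedule of required procedures. It marks "Subject Diary Review" and a count of returned product at Visit 2. Two rows below the diary review, "Adverse Experiences" has no mark at Visit 1 or Visit 2.

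**Visit lists.** The Visit 2 list in 10.2 opens with "Perform an abbreviated physical examination" and goes on to blood pressure, blood sampling, a 24-hour record, anthropometry and physical activity. The early withdrawal list in 10.3 opens with "Record any Adverse Experiences and/or review subject diary for adverse experiences and exclusionary medication use".

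**Safety text.** Section 11.2 states: "Using probiotic products doesn't cause any SAE". Section 11.1, under its severity heading, says earlier trials showed no severity problem with the product. Under its relationship heading it lists expected bowel symptoms. Section 11.2.1 nevertheless requires any serious event to be documented, related or not, and 17.2 requires reporting to the IRB irrespective of cause.

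**The concern.** A general rule to capture events throughout the study needs a step at which someone asks. Completers have no such step in either the schedule or the visit list, while the list for people who leave early has one. If staff work from 10.2, nothing prompts them to ask a completer about harms or to open the diary.

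Two things are at stake. First, non-serious events in completers may be under-recorded, and a favourable safety statement could partly reflect that. Second, ascertainment may depend on whether a participant withdraws. If withdrawal differs by arm, the comparison of event rates between arms is affected too.

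The advance statements in 11.1 and 11.2 add a separate problem. They stand where a severity scale and causality criteria would be expected, and they tell the assessor the answer to a question that 9.1.9 asks for each event.

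**Working it through.** No arithmetic settles this point, and the plan gives no figure to reproduce. The check sets the sections side by side.

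| Place | Adverse-event recording | Diary review | Count of returned product |
|---|---|---|---|
| 9.1.9 | required throughout | – | – |
| 8.7 | entered in diary by participant | diary brought to next visit | sachets brought to next visit |
| Appendix 1, Visit 1 | blank | not marked (diary started) | not marked |
| Appendix 1, Visit 2 | blank | marked | marked |
| 10.1, Visit 1 list | absent | absent | absent |
| 10.2, Visit 2 list | absent | absent | absent |
| 10.3, early withdrawal list | named | named, as an alternative or addition | absent |

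**Counts.** The adverse-event row is marked at 0 of 2 visits. Adverse-event recording is named in 1 of 3 visit lists, and completers do not follow that list.

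**How a site would read the blank row.** Appendix 1 has eight rows with no mark. Apart from the adverse-event row these are oximetry, spirometry, pregnancy test, hematology, ESR, C-reactive protein and urinalysis. Section 9 declares five of those seven inapplicable (9.1.6, 9.1.7, 9.2.1, 9.2.3, 9.2.4) and does not mention the other two. A blank row in this table therefore normally means that the procedure is not done.

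**What is left for completers.** Appendix 1 and 10.2 disagree on the diary review. If Appendix 1 is followed, diary entries are seen at Visit 2 but no open question is asked. If 10.2 is followed, neither happens. Either way, an event that the participant did not write down has no scheduled route to the case report form.

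**Timing.** Section 11.1 expects bowel symptoms in the first days, or one week at most. Section 15 puts the end of supplementation at 12 weeks. A symptom that ends with week 1 would be asked about at Visit 2 some 12 − 1 = 11 weeks later. An incomplete diary would then be hard to repair from memory.

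**Attribution.** Section 9.1.9 needs a severity grade and a relation for each event, and 11.1 supplies criteria for neither. Sections 11.2.1 and 17.2 make documentation and reporting of serious events independent of causality, so the sentence in 11.2 bears on attribution and not on capture.

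**Analysis.** Section 5.3 (Safety Evaluations) lists only expected biomarker changes, and section 15 contains no adverse-event table or comparison.

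**The case against.** A reader might infer from the blank row and the early withdrawal list that adverse events are collected only from people who withdraw. The documents do not support that. Section 8.7 gives every participant a diary that includes adverse events, Appendix 1 schedules its review at Visit 2, 9.1.9 applies to everyone, and 17.5 obliges the investigator to report any adverse event to the sponsor.

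A reader might also infer that 11.2 stops serious events being recorded. It does not: 11.2.1 and 17.2 apply whatever the cause.

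The contrast between completers and withdrawals can be overstated. The wording of 10.3 lets diary review alone satisfy its step, and 12.3 says only that people who leave early can have that visit. Procedures are the same in both arms, the trial is double-blind, and no withdrawal rate is given, so a difference between arms is a possibility and nothing more. Section 8.6 also ties product accounting to side effects and mentions checks in the first week. The contents list medical monitoring (11.4) and a safety management plan (11.5), whose text was not available for review, so nothing is claimed here about contact or monitoring between visits. Finally, Appendix 1 is headed as an example and keeps template placeholders.

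These points narrow the concern without removing it. Section 9 gives Appendix 1 the force of required procedures despite its heading. The diary review is absent from the list that staff would follow at Visit 2, and none of the sections cited supplies an active question to completers.

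**Conclusion.** The point stands as an internal contradiction with a practical consequence. Section 9.1.9 requires capture throughout, but Appendix 1 leaves the adverse-event row blank, and 10.2 omits both adverse-event recording and the diary review and sachet count that Appendix 1 marks at the same visit. Completers' non-serious harms therefore depend on a self-kept diary over about three months, and ascertainment may be incomplete and may differ from that in withdrawals. An effect on the comparison between arms would need the further assumption that withdrawal differs by arm.

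Separately, 11.2 and the severity text in 11.1 prejudge attribution and conflict with 9.1.9 and 11.2.1. Documentation and reporting of serious events remain intact.

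The number of events that could be missed cannot be estimated, because the documents give no event rate, withdrawal rate or diary completion rate. The conclusion assumes that Appendix 1 was extracted correctly and that the unavailable text of 11.4 and 11.5 adds no Visit 2 enquiry.

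**What to change.** 1. In Appendix 1, mark the adverse-event row at Visit 2.
2. In 10.2, add an open adverse-event question, together with the diary review and sachet count that Appendix 1 already schedules there.
3. Delete the sentence in 11.2 that rules out serious events in advance. Reconcile 11.1 with 9.1.9 by replacing the advance statements with a severity scale and causality categories, so that both are recorded for every event while the assessor is still blinded.
4. In section 15, add a table of adverse events by arm.

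The cost is a few minutes at a visit already held, some wording, and one extra table.
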